- c: Actual collection times should be collected in the electronic Case Report Form along with the times of the last dose administration.
- d: Triple ECG for the QT/QTc analysis after at least 10 minutes' rest and within 2 minutes and have to be taken before any blood sampling. See [Table 1](#) and [Table 2](#) for 12-lead Safety ECG timing (note that triple ECG for the QT/QTc analysis here is listed as 12-lead QTc Assessment in Tables 1 and 2).

Table 6 Schedule of Electrocardiogram, Pharmacokinetic, and Biomarker Assessments during Dose Expansion - Part B (for 21- and 28-day cycles)

Treatment Day ^a	Time h (± min) ^{b,c}	ECG ^d	PK M3258	PK dexamethasone	LMP7 activity & β5c	CCI
D1 C1	Predose		X		X	
	1 (± 5)		X			
	2 (± 10)		X		X	
	3 (± 15)		X			
	4 (± 15)		X			
	5 (± 15)		X			
	6 (± 15)		X		X	
D2 C1 ^f	24 (Predose)		X		X	
D8 C1	Predose	X	X		X	
	1 (± 5)		X			
	2 (± 10)	X	X		X	
	3 (± 15)		X			
	4 (± 15)	X	X			
	5 (± 15)		X			
	6 (± 15)	X	X		X	
D1 C2	Predose		X ^e	X ^e		
	1 (± 5)		X ^e	X ^e		
	2 (± 10)		X ^e	X ^e		
	3 (± 15)		X ^e	X ^e		
	4 (± 15)		X ^e	X ^e		
	5 (± 15)		X ^e			
	6 (± 15)		X ^e		X ^e	
	8 (± 30)		X ^e			

β5c = Constitutive proteasome subunit β5; C = Cycle; D = Day; ECG = Electrocardiogram; LMP7 = Large multifunctional protease 7; CCI [REDACTED]; Pd = Pharmacodynamics; PK = Pharmacokinetics.

a: Table 6 is applicable for all proposed regimens in Part B.

b: At visits where assessment time points (ECG, PK and PD) coincide with each other

- 1) Perform vital signs assessments at first
- 2) ECG assessments slightly before the specific collection time point
- 3) PK assessments at scheduled collection time point and
- 4) Pd assessments as last assessment

c: Actual collection times should be collected in the eCRF along with the times of the last dose administration.

- d: Triple ECG for the QT/QTc analysis after at least 10-minutes rest and within 2 minutes and have to be taken before any blood sampling. See [Table 3](#) and [Table 4](#) for 12-lead Safety ECG timing (note that triple ECG for the QT/QTc analysis here is listed as 12-lead QTc Assessment in Tables 3 and 4).
- e: PK samples for food effect evaluation taken for at least the first 18 participants. Decision on sampling in further participants will be taken during interim analysis.
- f: For participants in the safety run-in and the first 3 participants at a new dose.

2**Introduction**

Multiple myeloma is characterized by the presence of monoclonal plasma cells in bone marrow, extramedullary organs, or both. Symptomatic MM is defined by end organ damage such as lytic bone lesions, hypercalcemia, anemia, and renal impairment. Relapsed MM is defined as a recurrence of disease after prior response based on objective laboratory and radiological criteria. Refractory MM is defined as disease that becomes nonresponsive or progressive on therapy or within 60 days of last treatment in participants who had achieved a minimal response or better on prior therapy. Once relapse treatment is required, individual participant characteristics will influence the optimal treatment choice. The risk status must be determined based on established criteria. Twenty percent of participants have aggressive relapse according to IMWG criteria, based on unfavorable cytogenetics [del17p, t(4;14), add1q/del1p, t (14;16) and others, high-risk gene expression profile, high b-2-M] or low albumin, high-serum lactate dehydrogenase ([Sonneveld 2017](#)).

M3258 is a novel, orally-administered highly selective first in class inhibitor of the immunoproteasome subunit LMP7 that is being developed for the treatment of participants with RRMM.

The combination of M3258 with dexamethasone is expected to deliver increased efficacy with similar safety as compared to M3258 monotherapy. This is based on the precedent of clinical experience with pan-proteasome inhibitors in combination with dexamethasone.

Complete information on M3258 is in the Investigator's Brochure (IB).

2.1 Study Rationale

M3258 is an oral, potent and selective covalent-reversible inhibitor of the chymotrypsin-like activity of LMP7 (β 5i, PSMB8) subunit of the immunoproteasome, which has the potential to deliver a therapeutic benefit to patients with RRMM.

M3258 demonstrated potent and selective inhibition of LMP7 in human MM cell lines as well as in peripheral blood mononuclear cell (PBMCs) from various species including human. In contrast to the pan-proteasome inhibitors bortezomib, carfilzomib and ixazomib which indiscriminately inhibit multiple proteolytic subunits of the immunoproteasome and constitutive proteasome, M3258 demonstrated more than 500-fold biochemical selectivity for LMP7 versus the β 5c proteolytic subunit of the constitutive proteasome.

M3258 demonstrated strong antitumor activities, up to complete regressions, in nonclinical multiple myeloma models. Optimal efficacy was observed upon QD oral dosing of M3258, a schedule associated with sustained suppression of LMP7 activity in tumor cells and peripheral blood mononuclear cells. M3258 also demonstrated superior in vivo efficacy compared to the approved pan-proteasome inhibitors in different nonclinical models including cytogenetic high-risk models, suggesting the potential for M3258 to deliver an efficacy benefit to patients with MM who do not display an optimal response to these approved therapeutic agents.

LMP7 activity as Pd readout has been demonstrated in several nonclinical species and tissues. Nonclinical data from pharmacology, PK and toxicology studies suggest an acceptable safety profile and window of M3258 in humans. Clinical experience with pan-proteasome inhibitors

suggests no overlapping safety adverse events (AEs) in combination with dexamethasone and immunomodulatory imide drugs (IMiDs) and encouraging clinical antitumor activity in participants with MM.

2.2 Background

Treatment of newly diagnosed and relapsed myeloma has been a rapidly moving field because of an improved understanding of disease biology and access to new drugs (Kumar et al, 2018, Lonial et al, 2015). Prior combination attempts showed that combining multiple cytotoxic drugs would not improve therapy especially when combinations of alkylators with steroids were involved, which instead led to a more pronounced toxicity profile (Oken, 1997).

[figure not shown]
When the “novel” IMiDs and proteasome inhibitors (PIs) were brought to the field a decade ago, they subsequently demonstrated greater efficacy and were deemed safer in combinations, leading to a push to combine agents for newly diagnosed patients. This much-needed change is now extending to the relapse setting as well. Recent Phase III studies have suggested that combinations of these new agents with each other, or with alkylator based therapy, resulted in greater responses and prolonged duration of remission and OS (Cavo et al, 2011; Sonneveld et al, 2012; Stewart et al, 2015; Lonial et al, 2015). The ubiquitin-proteasome pathway is responsible for degradation of ubiquitinated proteins in eukaryotic cells, including proteins that control cell-cycle progression, apoptosis, and DNA repair and therefore, plays an essential role in maintaining normal cellular homeostasis (Micale et al, 2014). The immunoproteasome and constitutive proteasome are multi-subunit cylindrical complexes that process ubiquitinated proteins and generate peptides which can be presented on major histocompatibility complex Class I. In contrast to the constitutive proteasome, which is broadly expressed, the immunoproteasome is specifically present in normal hematopoietic cells and hematopoietic cancers such as MM. In normal and cancerous cells of nonhematopoietic origin, expression of the immunoproteasome is typically low, but can be induced by inflammatory conditions such as exposure to interferon gamma (Hallermalm et al, 2001).

Pan-proteasome inhibitors such as bortezomib, carfilzomib and ixazomib indiscriminately inhibit the proteolytic activities of multiple subunits of the immunoproteasome and constitutive proteasome (reviewed in Ettari et al, 2018). These agents are approved for use in patients with MM either as monotherapy or in combination with other agents such as IMiDs (e.g., lenalidomide) and the corticosteroid dexamethasone (reviewed in Brayer et al, 2017). Experimental data has indicated that pan-proteasome inhibitors elicit diverse effect on MM cells, which may potentially underpin their therapeutic efficacy (reviewed in Kubiczkova et al, 2014 and McBride et al, 2013). However, the lack of selectivity of these agents, in particular the inhibition of the constitutive proteasome in diverse tissues, is assumed to drive their adverse safety profiles, with common side effects such as peripheral neuropathy, cardiac disorders, gastrointestinal disturbances, fatigue and thrombocytopenia (reviewed in Ettari et al, 2018 and Cengiz Seval et al, 2018). Selective inhibition of the immunoproteasome may potentially maintain antitumor efficacy in MM, while circumventing the severe toxicities associated with pan-proteasome inhibitors (reviewed in Ettari et al, 2018 and Miller et al, 2014).

M3258 is an oral, potent, selective, covalent-reversible inhibitor of the chymotrypsin-like proteolytic activity of LMP7 (β 5i, PSMB8) subunit of the immunoproteasome. M3258 displays potent antitumor efficacy, up to complete tumor regression, in nonclinical models of MM, including models harboring the t(4;14)-translocation; a high-risk biomarker commonly

detected in patients with MM displaying poor prognosis and shorter time to progression (reviewed in Bustoros et al, 2017 and Sonneveld, 2017). Furthermore, M3258 demonstrates an improved therapeutic index compared to bortezomib, carfilzomib and ixazomib based on nonclinical animal safety studies. Finally, M3258 is orally bioavailable in animals and demonstrated a drug-drug interaction profile potentially compatible with combination with other agents such as dexamethasone.

CCI

[figure not shown]

Nonclinical studies in different species have confirmed that oral administration of M3258 results in inhibition of LMP7 activity in normal and in tumor tissue. An LMP7 activity assay as Pd readout in human PBMCs is currently validated for clinical use.

CCI

CCI

CCI

111

In the absence of clinical experience with M3258, all study participants will be monitored for any potential occurrence of a SAE irrespective to its attributability to study intervention. When necessary, M3258 administration should be discontinued and appropriate medical interventions initiated in accordance to local medical standards.

CCI

A large black rectangular redaction box covers the majority of the page content, from approximately y=85 to y=250. A small white rectangular area is located at the bottom center of the page, around y=850 to y=950.

CCII

To better understand and characterize the relevant toxicities, in addition to ensuring safety of clinical study participants, AEs such as GI hemorrhage, GI mucositis (diarrhea, vomiting),

[figure not shown]
opportunistic infections and allergic reactions/hypersensitivity will be considered adverse events of special interest (AESI) and a guidance, in line with standard medical practices, to manage such toxicities are provided in Sections 6.9 and 6.9.1.

During clinical study, a SMC will provide recommendations on dose and regimens during dose escalation based on review of study participant's available data (clinical and PK) in consideration of an anticipated steep dose-response toxicity as well as the potential toxicity due to accumulation over time.

Combination of M3258 with Dexamethasone

Pan-proteasome inhibitors such as bortezomib, carfilzomib and ixazomib are approved in various countries for use in patients with MM in combination with other agents such as the corticosteroid dexamethasone. A detailed retrospective analysis of safety and efficacy signals from multiple second-line clinical studies in participants with MM using either bortezomib or the combination of bortezomib with dexamethasone was published (Dimopoulos et al, 2015). This analysis concluded that the combination of bortezomib with dexamethasone delivered a greater efficacy versus bortezomib monotherapy, exemplified by higher overall response rate (ORR) (75% vs. 41%; odds ratio = 3.467; $P < 0.001$) and longer median time-to-progression (13.6 vs. 7.0 months; hazard ratio [HR] = 0.394; $P = 0.003$) and PFS (11.9 vs. 6.4 months; HR = 0.595; $P = 0.051$). Furthermore, the rates of any-grade AEs, most common Grade 3 or higher AEs, and discontinuations due to AEs were comparable in participants receiving bortezomib with dexamethasone compared to bortezomib monotherapy. These findings were broadly supported by a second publication (Harrison et al, 2015).

CCI

Based upon available nonclinical data from M3258 and known class effects from approved pan-proteasome inhibitors, the measures for safety reporting, safety monitoring, and risk mitigative activities for this proposed FiH study are considered adequate.

Further, dexamethasone at a cumulative dose of 40mg/week will be administered in the established low-dose regimen in the expansion part of the study, as is used in standard of care in combination with the oral pan-proteasome inhibitor ixazomib.

3 Objectives and Endpoints

Table 7 Study Objectives and Endpoints - Dose Escalation- Part A

Objectives	Endpoints (Outcome Measures)
Primary	

 To determine safety, tolerability and the MTD (if observed) of M3258 as a single agent in participants with RRMM 	
 Occurrence of DLTs in participants with RRMM receiving M3258 as a single agent during the DLT period Occurrence of any AEs reported (serious or nonserious) will be considered TEAEs and TRAEs (including TEAEs leading to death or discontinuation of treatment) in participants receiving M3258 as a single agent from start of study intervention to 30 days after End of Study Intervention Occurrence of TEAEs outside of the DLT period that SMC deems relevant for determination of the MTD Study treatment-emergent changes in clinical laboratory measures from Baseline, safety ECGs measures, vital signs, ECOG performance status in participants receiving M3258 as a single agent from start of study intervention to 30 days after end of study intervention
Secondary	

 To investigate the PK profile of M3258 (single and multiple dose exposure) in participants with RRMM 	
 PK profile of M3258 in terms of C_{max}, AUC_{0-t}, AUC_{0-24} at Day 1, Cycle 1, (single dose): predose, 1, 2, 3, 4, 5, 6, 8 and 24 h after administration PK profile of M3258 in terms of C_{max}, AUC_{0-24} at Day 8 Cycle 1, (multiple dose): predose, 1, 2, 3, 4, 5, 6, and 8 h after administration

 To investigate the recommended dose and regimen for expansion (RDE) in participants with RRMM 	
 In addition to safety, tolerability and PK, for selection of recommended dose and regimen for expansion (RDE), changes in Pd (LMP7 activity) in pre and post study intervention samples on Day 1 Cycle 1 pre and postdose, Day 2 Cycle 1 predose and Day 8 Cycle 1 pre and postdose

Objectives	Endpoints (Outcome Measures)
	
 Changes from Baseline in serum M-protein, urine M-protein, or free light chain protein levels (for free light chain disease) on Day 1 of every cycle

 To evaluate preliminary clinical activity using IMWG criteria 	
 OR, DOR, Time to Response until CR, sCR, VGPR or PR according to IMWG
Exploratory	

 To investigate the changes in the Pd marker of M3258 as a single agent in participants with RRMM 	
 Changes in Pd (LMP7 activity) in pre and post study intervention samples on Day 1 Cycle 1 pre and postdose, Day 2 Cycle 1 predose and Day 8 Cycle 1 pre and postdose

 To investigate further PK parameters of M3258 (single and multiple dose exposure) in participants with RRMM 	
 PK profile of M3258 in terms of t_{max}, t_{lag}, $t_{1/2}$, CL/F, V_z/F at Day 1 Cycle 1, (single dose): predose, 1, 2, 3, 4, 5, 6, 8 and 24 h after administration PK profile of M3258 in terms of $AUC_{0-\infty}$ (if calculable), t_{max}, t_{lag}, $t_{1/2}$, CL_{ss}/F, at Day 8 Cycle 1, (multiple dose): predose, 1, 2, 3, 4, 5, 6 and 8 h after administration PK profile of M3258 in terms of C_{trough} at Days 8 and 15 (QD regimen only) Cycle 1: predose PK profile of M3258 in terms of R_{acc} (AUC) and R_{acc} (C_{max}) after Day 1 (single dose) and Day 8 (multiple dose), Cycle 1 and dose-normalized C_{max}, AUC_{0-t}, AUC_{0-24} for single and multiple dose

 To investigate the relationship between exposure of M3258 as a single agent and QTc in participants with RRMM 	
 Relative changes from Baseline in ECG parameter QTc in relation to M3258 plasma concentration: all times after single and multiple dosing with concurrent QTc and plasma concentration assessments

 To investigate genetic variations that may affect PK of M3258 as a single agent 	
 Assessment of genetic variations that affect drug metabolism and drug transport of M3258 and other potential genes that may account for differences in the PK profile

Objectives	Endpoints (Outcome Measures)

 To explore potential metabolites of M3258 in plasma in participants with RRMM 	
 Assessment of potential metabolites of M3258 in plasma

 To explore L-citrulline as an exploratory biomarker 	
 Changes in the L-citrulline blood levels during the study at Day 1 and Day 15 predose, Cycle 1, and Day 1 predose, Cycle 2 and Cycle 3

 To investigate relationship of drug treatment and Minimal Residual Disease (MRD) in participants with RRMM 	
 Assessment of MRD upon CR or sCR

Table 8

Study Objectives and Endpoints - Dose Expansion - Part B

Objectives	Endpoints
Primary	

 To determine safety and tolerability of M3258 at the recommended dose and regimen for expansion (RDE) when co-administered with dexamethasone in participants with RRMM To determine recommended Phase II dose of M3258 when co-administered with dexamethasone in participants with RRMM based on early signs of safety and efficacy in the expansion phase 	
 Occurrence of dose-limiting toxicities (DLTs) in participants receiving M3258 in combination with dexamethasone during the DLT period Occurrence of study treatment-emergent SAEs including deaths from first dose of study intervention to 30 days after end of study intervention Occurrence of TEAEs and TRAEs (including deaths) from start of study intervention up to 30 days after end of study intervention Study treatment-emergent clinically relevant abnormal changes in clinical laboratory measures from Baseline, ECGs measures, vital signs, ECOG performance status from start of study intervention to 30 days after end of study intervention Occurrence of TEAEs and TRAEs (including deaths) in participants receiving M3258 when given in combination with dexamethasone from start of study intervention to 30 days after end of study intervention

Objectives	Endpoints
	
 • OR, DOR. Time to Response until CR, sCR, VGPR, or PR according to IMWG
Secondary 
 • To collect preliminary efficacy data in participants with RRMM under treatment with M3258, when co-administered with dexamethasone 	
 • OR, DOR. Time to Response until CR, sCR, VGPR, or PR according to IMWG • Progression-Free Survival (PFS) per Investigator • Overall Survival (OS) censored at End of Study

 • To investigate the PK profile of M3258 (single and multiple dose exposure) when co-administered with dexamethasone in participants with RRMM 	
 • PK profile of M3258 in terms of C_{max}, AUC_{0-t}, AUC_{0-24} at Day 1 Cycle 1, (single dose): predose, 1, 2, 3, 4, 5, and 6 and 24h after administration • PK profile of M3258 in terms of C_{max}, AUC_{0-24} at Day 8 Cycle 1, (multiple dose): predose, 2, 4, and 6h after administration
Exploratory 
 • To investigate the changes in the pharmacodynamic marker of M3258 when co-administered with dexamethasone in participants with RRMM • To investigate further PK parameters of M3258 (single and multiple dose exposure) when co-administered with dexamethasone in participants with RRMM • To investigate the food effect on the PK of M3258 when co-administered with dexamethasone in participants with RRMM 	
 • Changes in LMP7 activity on Day 1 Cycle 1 pre and postdose and Day 8 Cycle 1 pre and postdose • PK profile of M3258 in terms of t_{max}, t_{lag}, $t_{1/2}$, CL/F, V_z/F at Day 1 Cycle 1, (single dose): predose, 1, 2, 3, 4, 5, 6 and 24h after administration • PK profile of M3258 in terms of $AUC_{0-\infty}$, t_{max}, t_{lag}, $t_{1/2}$, CL_{ss}/F, at Day 8 Cycle 1, (multiple dose): predose, 2, 4, and 6 h after administration • PK profile of M3258 in terms of dose-normalized C_{max}, AUC_{0-t}, AUC_{0-24} for single and multiple dose • Area under the plasma concentration-time curve (AUC_{0-8h}) with and without food from time zero (= dosing time) to 8 h and C_{max} of M3258 observed on Day 1 Cycle 2: predose, 1, 2, 3, 4, 5, 6 and 8 h postdose

Objectives	Endpoints

 To investigate the relationship between exposure with M3258 and QTc, when co-administered with dexamethasone in participants with RRMM 	
 Relative changes from Baseline in ECG parameters (QTc) in relation to M3258 plasma concentration: all times after single and multiple dosing with concurrent QTc and plasma concentration assessments

 To investigate genetic variations that may affect PK of M3258, when co-administered with dexamethasone in participants with RRMM 	
 Assessment of genetic variations that affect drug metabolism and drug transport of M3258 and other potential genes that may account for differences in the PK profile

 To explore potential metabolites of M3258 in plasma, when co-administered with dexamethasone in participants with RRMM 	
 Assessment of potential metabolites of M3258

 To investigate the PK profile of dexamethasone when co-administered with M3258 in participants with RRMM 	
 Area under the plasma concentration-time curve (AUC_{0-8h}) from time zero (= dosing time) to 8 h and C_{max} of dexamethasone observed on Day 1, Cycle 2: predose, 1, 2, 3, 4, and 6 h postdose

 To explore L-citrulline as an exploratory biomarker 	
 Changes in the L-citrulline blood levels during the study at Day 1 and Day 15 predose, Cycle 1, and Day 1 predose, Cycle 2 and Cycle 3

 To investigate change β5c activity after M3258, when co-administered with dexamethasone in participants with RRMM 	
 Changes in β5c activity on Day 1 Cycle 1 pre and postdose and Day 8 Cycle 1 pre and postdose

 To investigate relationship of drug treatment and MRD, when M3258 is co-administered with dexamethasone in participants with RRMM 	
 Assessment of MRD upon CR or sCR

4 Study Design

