Serum M-Protein Electrophoresis	X	X				X			X		X	X	X	X	X		See Section 8 and Appendix 7	
Quantitative Urine Ig (immunofixation in 24h urine)	X																When CR is suspected and no detectable M-Protein in serum	
Urine M-Protein Electrophoresis (in 24 h urine sample)	X	X				X			X		X	X	X	X	X		See Section 8 and Appendix 7	
In Case of Free Light Chain Disease: Free Light Chain in Serum		X				X			X		X	X	X	X	X		For participants with common MM, the free light chain in serum will be tested when CR is suspected	

AE = Adverse event, BID = twice daily, Ca = Calcium, CT = Computed tomography, CV = Cardiovascular, CR = Complete response, HIV = Human immunodeficiency virus, ECG = Electrocardiogram, ECOG = Eastern Co-operative of Oncology Group, Ig = Immunoglobulin, IMWG = International Myeloma

CONFIDENTIAL
INFORMATION

34/155

M3258

First in Human Dose Escalation of M3258 as a Single Agent and Expansion Study with M3258 in Combination with Dexamethasone

MS201814-0010

Working Group, MRI =Magnetic resonance imaging, MRD = Minimal residual disease, MUGA = Multigated acquisition, NGS = Next-Generation-Sequencing, PK = Pharmacokinetics, Pd = Pharmacodynamics, PR = Partial response, QD = Once daily, SAE = Serious adverse event, WOCBP = Women of childbearing potential.

Table 3 Schedule of Activities – Dose Expansion - Part B (for 28-day cycles)

Assessments & Procedures	Screening	Intervention Period														End of Study Intervention	Follow-Up / Discontinuation	Notes	
		Cycle 1		Cycle 2		Cycle 3		Cycle 4	Cycle 5	Cycle 6	Every cycle after Cycle 6								
	Up to 28 days before Day 1 Cycle 1	Day	1	2	8	15	22	1	8	15	22	1	15	1	1	1	within 7 days of intervention/intake	30 days, after last dose	Day 2 Cycle 1 visit is only for participants in safety run-in or the first 3 participants at a changed dose.
Assessments & Procedures	Visit Window		± 1 d	± 1 d	± 3 d	± 3 d	± 3 d	± 7 d	± 3 d	± 7 d	d = days								
	Informed Consent	X																	
	Inclusion and Exclusion Criteria	X	X																Recheck clinical status before first dose of study intervention.
	Demography/Height	X																	
	Physical Examination with Weight	X	X	X a	X a	X a	X	X a	X a	X a	X a	X a	X a	X a	X			Details in Section 8.2.1. a = brief physical examination including peripheral motor and sensory nervous system	

Assessments & Procedures	Screening	Intervention Period														End of Study Intervention	Follow-Up / Discontinuation	Notes	

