The SMC will recommend a dose and regimen for the expansion cohort based on an integrated review on all available safety, tolerability, PK, Pd (including LMP7 activity) and initial efficacy data.

Residual LMP7 activity reaching a plateau comparing at least 3 increasing dose levels will support the RDE selection.

At least 6 participants need to be treated at the selected RDE as M3258 monotherapy. Additionally, the median estimated DLT rate of the RDE needs to be $\leq 25\%$ and the 75% percentile of the estimated DLT probability of the RDE needs to be below 30%.

If further data is required to determine the RDE, additional participants may be enrolled in Part A (see Section 9.2).

Dose Expansion Part B

Once an RDE (dose and regimen) of M3258 has been defined which is considered safe by the SMC, dose expansion (Part B) may begin. Initiation of Part B may start without reaching the MTD in Part A; dose escalation for defining the monotherapy MTD (Part A) may proceed in parallel.

Participants with MM whose disease has progressed following > 3 lines of therapy for whom no effective standard therapy exists (see definition in Section 5) will be enrolled. In Part B, participants will receive M3258 at the RDE selected in Part A in combination with dexamethasone at a cumulative dose of 40 mg / week. The first 2 cohorts of 3 participants each (first 6 participants) will be used for a safety run-in. The participants in these 2 cohorts will be enrolled in a staggered approach. Each cohort of the safety run-in will be evaluated by the SMC for the prespecified DLT criteria (see Section 6.6) of this combination before additional participants are enrolled. The SMC meetings will be held after the first 3 and 6 participants have finished Cycle 1 or discontinued treatment. The SMC will evaluate safety, cumulative

and unacceptable toxicity (see definition of acceptable toxicity below). SMC decisions on potential dose adjustments in the safety run-in (and later on) will be supported by Bayesian modeling. After the safety run-in, SMC meetings will be held at the completion of Cycle 1 or discontinuation of treatment for every 6 participants (without pausing enrollment) in order to assess safety, cumulative and unacceptable toxicity of all participants in the expansion cohort, unless a change in dosing has occurred. In case dosing in the expansion cohort was changed, the next SMC will be held after 3 participants have finished the DLT period or discontinued.

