9.2 Sample Size Determination

Dose Escalation Part A

The planned cohort size is 3 participants at a given dose. Parallel screening and enrollment of participants will allow eligible participants to enroll, the cohort size may therefore increase to a maximum of 4 participants. Any additional participants enrolled in the study at a given dose, will complete all study procedures and assessments as per protocol and are considered in the Bayesian model if they fulfill the criteria for inclusion in the DLT set.

The total sample size will depend on the number of cohorts and regimens to be evaluated. It is anticipated that 15 to 21 participants (4 projected dose levels with 3 to 9 participants each) may be needed. If change(s) in regimen would occur, the sample size may increase.

The following scenario is anticipated:

2 dose levels with 3 participants each and 2 dose levels with 6 participants each, resulting in 18 participants.

Considering for example one change in regimen after the first dose level, the sample size may increase by 3 if in the new regimen, the above scenario holds.

Dose Expansion Part B

Part B begins with a safety run-in of 6 participants. Dose adjustments during Part B may occur.

Part B will include 30 participants treated at the same dose who are evaluable for response in a two-stage design. This sample size will give a posterior probability of 85% that the ORR \geq 20% if 8/30 responses are seen at the final analysis.

An interim analysis will occur after enrollment of 15 participants treated at the same dose are evaluable for response. The cut-off for the interim analysis was chosen to balance sufficient information for decision with the potential of sparing participants an inefficient treatment. The boundary and operational characteristics are described in Section 9.4.1.

If in the course of the expansion and/or at the interim analysis, the M3258 dose is modified, then only participants treated at the same dose will be considered in the two-stage design. Therefore, the number of participants in the expansion cohort might increase by approximately 3 to 21 participants to reach the required number of 30 participants treated on the same dose who are evaluable for response according to IMWG.

Additionally, in Part B (as well as in Part A) the SMC may recommend to end the enrollment in the expansion cohort due to safety concerns.

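### Two Part B PK endpoints do not match their scheduled samples: dexamethasone AUC0-8h stops at 6 h, and the Day 1 24 h M3258 sample behind AUC0-t and AUC0-24 is taken only in a subset

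*Protocol*

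**What the plan says.** **Dexamethasone.** Protocol Section 3, Table 8 (Part B, exploratory) defines the AUC "from time zero (= dosing time) to 8 h and C_{max} of dexamethasone observed on Day 1, Cycle 2", and lists the samples as "of dexamethasone observed on Day 1, Cycle 2: predose, 1, 2, 3, 4, and 6 h postdose". In Table 6 (Section 1.3) the Day 1 Cycle 2 schedule has an 8 h row that is marked for M3258 and not for dexamethasone. Footnote e applies to the marks of both drugs on that day and guarantees the sampling for at least the first 18 participants. The SAP (Section 5, Part B table) repeats the 8 h AUC with samples to 6 h.

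**M3258, Day 1 Cycle 1.** The synopsis and Table 8 (Part B, secondary) list Cmax, AUC0-t and AUC0-24, with Table 8 giving the sampling "at Day 1 Cycle 1, (single dose): predose, 1, 2, 3, 4, 5, and 6 and 24h after administration". Neither place restricts who gives the 24 h sample. Table 6 footnote f does restrict it: "For participants in the safety run-in and the first 3 participants at a new dose". The notes to the Part B schedules (Tables 3 and 4) agree: "Day 2 Cycle 1 visit is only for participants in safety run-in or the first 3 participants at a changed dose". Part B has no 8 h sample on Day 1 Cycle 1, so everyone outside that subset has a last sample at 6 h.

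**Definition of AUC0-t.** Protocol Appendix 8 runs it to each participant's last sample at or above the quantification limit, so the length of the window depends on which samples are taken.

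**The concern.** An AUC over a stated interval needs samples that reach the end of that interval, or a stated rule for the part not sampled. Neither endpoint has this.

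For dexamethasone, the last 2 of the 8 hours are unsampled, although blood is drawn at 8 h on that day for the other drug. The M3258 food-effect endpoint on the same day has the same 0-8 h window and does list an 8 h sample, so the gap is specific to dexamethasone.

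For M3258 on Day 1, a Part B summary of AUC0-t would combine participants followed to 24 h with participants followed to 6 h. Its mean and spread would partly describe length of sampling rather than exposure. AUC0-24 has no 24 h sample in most participants, and no rule says how to obtain it. The integrated analysis plan for the SMC (SAP Appendix 18.1, Section 16.1) carries the predose value forward as the 24 h value, but for multiple dosing only.

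**Working it through.** The documents state no figure that depends on this point, so there is none to reproduce. The check has three steps.

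**1. Windows against samples (Tables 6 and 8)**

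| Endpoint | Window | Last scheduled sample | Unsampled |
|---|---|---|---|
| Dexamethasone AUC, Day 1 Cycle 2 | 0-8 h | 6 h | 2 of 8 h |
| M3258 AUC0-24, Day 1 Cycle 1, with the Day 2 visit | 0-24 h | 24 h | none beyond the last sample |
| M3258 AUC0-24, Day 1 Cycle 1, without the Day 2 visit | 0-24 h | 6 h | 18 of 24 h |
| M3258 food-effect AUC0-8h, Day 1 Cycle 2 | 0-8 h | 8 h | none beyond the last sample |

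In the readable copy of Table 6, the second mark in the 6 h row of Day 1 Cycle 2 falls under the LMP7 column. That may be a fault in how the table was read. Either way, no dexamethasone sample is scheduled after 6 h, and Table 8 and the SAP both say so in words.

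**2. Participants without the 24 h sample**

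The run-in is 6 participants (Protocol Section 4.1: "The first 2 cohorts of 3 participants each (first 6 participants) will be used for a safety run-in"). The target is 30 (Section 9.2: "Part B will include 30 participants treated at the same dose who are evaluable for response in a two-stage design").

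- No dose change: 30 − 6 = 24 without a 24 h sample; 24/30 = 80%.
- At a changed dose: 30 − 3 = 27 without it; 27/30 = 90%.
- All of Part B with one dose change and 3 to 21 extra participants (Section 9.2): (6 + 3)/33 = 27% down to (6 + 3)/51 = 18% have it.

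**3. What the window length does (illustration only)**

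The readable text gives no half-life or absorption rate for either drug. Assume a one-compartment oral model with ka = 1 per h and k = ln 2 / half-life. Apart from a constant that cancels in ratios,

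AUC(0-t) = ka/(ka − k) × [(1 − e^(−kt))/k − (1 − e^(−ka·t))/ka].

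| Assumed M3258 half-life | AUC0-6 | AUC0-24 | AUC0-6/AUC0-24 | Fold difference |
|---|---|---|---|---|
| 2 h | 2.34 | 2.88 | 0.81 | 1.2 |
| 6 h | 3.77 | 8.04 | 0.47 | 2.1 |
| 12 h | 4.32 | 12.72 | 0.34 | 2.9 |
| 24 h | 4.65 | 16.80 | 0.28 | 3.6 |

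For dexamethasone, the share of AUC0-8 that lies after 6 h is 1 − AUC0-6/AUC0-8:

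- half-life 3 h: 1 − 2.92/3.44 = 15%
- half-life 6 h: 1 − 3.77/4.77 = 21%

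**Could the terminal slope fill the gap?** SAP Section 16.1.1.2 asks for at least 3 points, excluding Cmax, spanning at least 2 half-lives where possible, and flags shorter spans. With hourly samples to 6 h and Cmax no earlier than 1 h, the usable span is at most 2 to 6 h, which is 4 h. Under that criterion, any half-life above 4/2 = 2 h would be flagged. The SAP wrote this rule for the Part A analysis; it is used here only as a yardstick.

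**The case against.** **The sparser sampling is deliberate, and the analysis is descriptive.** Full Day 1 sampling in the run-in and at a new dose, with fewer samples afterwards, is written into the schedules. Protocol Section 9.4 calls all analyses descriptive, and the SAP leaves most Part B PK entries to a later version. SAP Section 16.1.1 calculates parameters only where applicable and uses a fixed-window AUC0-8, and Section 16.1.1.3 allows an AUC to a fixed time when AUC0-∞ fails. The team could therefore simply have left AUC0-24 unreported where there was no 24 h sample. This stands as far as it goes: extrapolation is not compelled. It does not reconcile Table 8 with Table 6, and it leaves AUC0-t, which can be calculated in everyone, with mixed windows.

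**The size is uncertain.** This stands. The fold difference rests entirely on assumed half-lives, and at 2 h it is small. The mixing also requires a quantifiable 24 h concentration. With a short half-life there may be none, and the windows would then agree.

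**The 8 h tube is guaranteed only for the first 18 participants.** This fails. The dexamethasone marks carry the same footnote, so participants with dexamethasone samples have the 8 h M3258 draw as well. Whether that tube holds enough plasma for both assays cannot be judged from these documents.

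**Stronger readings to avoid.** A reader might infer that the 24 h sample is confined to the run-in; the schedules also give it to the first 3 participants at a new dose. A reader might infer that a comparison of Part A with Part B is biased. Part A does sample everyone to 24 h, so a naive AUC0-t comparison would make Part B look lower, but no such comparison is prespecified. Nor is the M3258 food-effect AUC0-8h affected, because M3258 is sampled at 8 h on that day.

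**Conclusion.** Both mismatches are real. The dexamethasone AUC0-8h has no sample in its last 2 h. The Day 1 M3258 AUC0-t and AUC0-24 are listed without restriction, yet the 24 h sample would be missing in 24 of 30 participants with no dose change and in 27 of 30 at a changed dose. Where the 24 h concentration is quantifiable, AUC0-t would mix 24 h and 6 h windows, and no rule covers Day 1 AUC0-24 without that sample.

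The counts follow from the documents. The 1.2- to 3.6-fold range and the 15% to 21% do not: they illustrate what assumed half-lives would imply.

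The point is minor. It touches one exploratory and one secondary PK endpoint, and no DLT rule, interim boundary or sample size. The SAP (Sections 5 and 7) records that the study stopped before Part B began, so no reported result is affected. What remains is a protocol text that should be corrected before it is reused.

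**What to change.** - **Dexamethasone:** add the 8 h time point for dexamethasone on Day 1 Cycle 2 in Tables 6 and 8, using the sample already drawn for M3258 if the plasma volume allows. Otherwise rename the endpoint AUC0-6h.
- **M3258, Day 1 Cycle 1:** make Cmax and AUC0-6h the Part B parameters for all participants. Report AUC0-t and AUC0-24 only in those with the 24 h sample, and say so in the synopsis and Table 8.
- **If Parts A and B are ever compared on Day 1:** use AUC0-6h in both. Everyone in either part is scheduled for samples to 6 h.
- **SAP:** align the Part B table in Section 5, which still lists Day 1 AUC0-t with samples to 6 h and no AUC0-24.

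The cost is changed table and endpoint wording and, if the first option is taken, one more dexamethasone assay per sampled participant. No visit or blood draw is added, provided the existing 8 h tube is large enough.
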